Using 152 MSM iTAB subjects categorized into perfect (37), high (n=85) and moderate (n=40). Those found 37 (24%) reporting perfect adherence in the past 34 days (representing two TFV-DP half lives) with mean TFV-DP concentrations of 1457 fmol/punch +/-694 fmol/punch. This corresponds almost exactly with predicted DBS concentrations for drug exposure of 7 doses per week in controlled pharmacokinetic studies where perfect adherence was associated with a level of 1460 fmol/punch (39). These data can therefore be used as the comparison to data derived in transgender women on csHT with perfect adherence by iTAB.

Sub-study IV Background and Significance

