At Weeks 0, 12, and 48, applicable subjects will complete the Body Image Scale (mBIS) questionnaire, and answer questions about general hormone therapy satisfaction.

SUB-STUDY STATISTICAL CONSIDERATIONS

Sample Size and Power

The primary aim of this analysis is to determine if PrEP interacts with hormone therapy in either direction that would impact either i) efficacy of PrEP to reduce HIV acquisition or ii) hormones to achieve desirable gender traits. Of our 300 person cohort, we estimate that 280 individuals will be MAAB Of those 280 MAAB, we predict that 70% will be taking feminizing hormones (n=196) and 30% will be on no hormonal therapy (n=84), based on previous population estimates (97). Based on adherence results in individuals randomized to iTAB (98), we estimate that 25% of participants will have perfect adherence to PrEP.

[figure not shown]

Figure 2: Predicted Numbers of Individuals on HRT and PrEP

Statistical power is based on a one-sample non-inferiority test to see if the TFV-DP concentration of perfectly adhered MAAB persons is equivalent to MSMs on average under an acceptable margin. The following assumptions are made: i) Using PK modeling of HIV-uninfected men and women, it has been shown that perfect adherers (i.e. daily dosing for 7 days) have TFV-DP concentrations of 1560 (IQR 1246-2029) fmol/punch as determined in MSM; ii) Since this is a non-inferiority study, we will assume the expected sample mean for MAAB is around 1560 fmol/punch, or slightly lower. In other words, we will assume the mean difference in TFV-DP concentrations between MAAB and MSMs is approximately 0 (ranges from -180 to 50); and iii) We believe that a difference of less than 230 fmol/punch (equivalent to 1 tablet per week dosing) in the TFV-DP concentration can be considered non-inferiority which will be the lower limit of acceptable variation. Thus, we will set the non-inferiority margin to be 230.

Assuming the standard deviation is 350, if the true mean TFV-DP concentration for MAAB is 1360 fmol/punch (ie, 100 fmol/punch lower than MSMs), then 45 subjects are required to be 80% confident that the lower limit of a one-sided 95% confidence interval of the mean difference between MAAB and MSMs will be above the non-inferiority limit of -230.

Analysis Plan

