The primary outcome is the intracellular TFV-DP levels, as measured in DBS, which is a continuous variable. Comparison between the MAAB and the existing MSM data that will be compared using a two-sample t-test. Differences in the means between the two groups, along with the standard deviations (SD) and their 95% confidence intervals will be reported. As a secondary/sensitivity analysis, multiple regression analysis will be performed to study the association between clinical and demographic factors (age, race, ethnicity, education, socioeconomic status, sexual risk behaviors, substance use, depression, concomitant medications) and group, adjusting for baseline demographic, stratification variables, and clinical characteristics. Variables significantly associated with both group and outcome (p<0.10) will be included in a multiple regression model as covariates.

For the main secondary hypothesis, in MAAB on csHT, to determine the change between baseline and week 12 estradiol levels in individuals taking PrEP and receiving stable estrogen replacement (controlling for route, dose and formulation), we will use a paired t-test. As estradiol concentrations can be unpredictable, we will measure estradiol concentrations in individuals choosing not to initiate PrEP at the same time points. Similar to 3A, multiple regression models will be developed if there are factors that require adjustment in this model.

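### Sub-study I: the only adjusted analysis of the comparison with the external MSM cohort selects covariates by a double p<0.10 screen, which at about 49 versus 37 people drops a large share of small-to-moderate confounders

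*Combined protocol and SAP*

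**What the plan says.** In Section 9, under the Sub-study I Analysis Plan, the primary analysis is unadjusted: "Comparison between the MAAB and the existing MSM data that will be compared using a two-sample t-test". The comparator is a previous text-messaging PrEP cohort, described under Preliminary Data in Section 7, so the groups are not randomized.

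The regression comes next and has a lower status: "As a secondary/sensitivity analysis, multiple regression analysis will be performed to study the association between clinical and demographic factors". The same sentence names nine candidate factors, from age and race to substance use and concomitant medication, and ends "adjusting for baseline demographic, stratification variables, and clinical characteristics". The entry rule follows: "Variables significantly associated with both group and outcome (p<0.10) will be included in a multiple regression model as covariates".

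The group sizes can be derived. Of 280 MAAB participants, "we predict that 70% will be taking feminizing hormones (n=196"), and "we estimate that 25% of participants will have perfect adherence to PrEP". For the comparator, "Those found 37 (24%) reporting perfect adherence in the past 34 days", with "mean TFV-DP concentrations of 1457 fmol/punch +/-694 fmol/punch".

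**The concern.** A confounder biases the group difference according to its imbalance between groups and its relation to the outcome. A significance screen looks instead at whether each of those two links is detectable in the sample, and the variable must pass twice. In small groups a real confounder can easily fail one of the two tests.

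The screen also interacts with the quantity being estimated. If TFV-DP is truly lower in participants on hormones and a confounder pushes the other way, the true difference weakens the crude covariate–outcome association. The covariate is then more likely to be discarded in the very situation the sub-study is meant to detect.

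At stake is the value of the adjusted result as a check on the t-test. If the screen empties the model, the adjusted analysis becomes the unadjusted one again, and agreement between the two says little.

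The text also allows two readings: a fixed adjustment with screened variables added, or screening alone. Two analysts could fit different models.

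**Working it through.** **Inputs from the documents.** MAAB on hormones with perfect adherence: 196 × 0.25 = 49. MSM comparator with perfect adherence: 37. Total 86. Planning SD 350, comparator SD 694, margin 230, assumed true difference −100 (Section 9, sub-study Sample Size and Power; Section 7, Preliminary Data).

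**Inputs assumed.** The documents give neither the covariate imbalance d (in SD) nor the covariate–outcome correlation r. I take d from 0.3 to 0.5 and r from 0.2 to 0.3, with one normal covariate at a time unless stated and everyone analysable.

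**Step 1: the plan's own figure.** n = [350 × (1.645 + 0.842) / (230 − 100)]² = 44.8, rounded up to 45. This reproduces the stated sample size. The plan gives no figure for the covariate screen.

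**Step 2: passing the group screen.** Two-sample t-test, two-sided p<0.10, noncentrality d / √(1/49 + 1/37) = d / 0.218. Power is 0.39 at d=0.3, 0.57 at d=0.4 and 0.74 at d=0.5.

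**Step 3: passing the outcome screen.** Fisher z, n=86: power ≈ Φ(atanh(r) × √83 − 1.645). This gives 0.58 at r=0.2, 0.75 at r=0.25 (0.77 by noncentral t) and 0.88 at r=0.3.

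**Step 4: passing both (product).**

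| d | r | kept | dropped |
|---|---|---|---|
| 0.5 | 0.3 | 0.74 × 0.88 = 65% | 35% |
| 0.4 | 0.3 | 0.57 × 0.88 = 50% | 50% |
| 0.4 | 0.25 | 0.57 × 0.75–0.77 = 43–44% | about 56% |
| 0.3 | 0.3 | 0.39 × 0.88 = 35% | 65% |
| 0.3 | 0.2 | 0.39 × 0.58 = 23% | 77% |

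Simulation with 40,000 runs per scenario agrees within about two percentage points for the pairs simulated (all except d=0.4, r=0.25). Strong confounders are kept: 98% at d=0.8, r=0.5.

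**Step 5: when TFV-DP is truly lower.** With a true difference of −100 (SD 350) opposing the confounding, retention falls from about 65% to 60% at d=0.5, r=0.3, and from about 50% to 47% at d=0.4, r=0.3. With a true difference of −230, retention at d=0.4, r=0.25 is 26–42% per covariate.

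**Step 6: bias.** With no adjustment, bias = d × r × SD. At d=0.4, r=0.25 this is 0.4 × 0.25 × 350 = 35, or 0.4 × 0.25 × 694 = 69 fmol/punch. The screened estimator does better, because some samples do adjust and the samples that miss the covariate tend to have the smaller imbalances. Simulated mean bias after screening, one confounder, d=0.4, r=0.25:

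| true difference | SD 350 | SD 694 |
|---|---|---|
| 0 | about 9 | about 20 |
| −100 | about 13 | about 23 |
| −230 | about 18 | about 27 |

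That is roughly 10–27 fmol/punch, or about 4–12% of the 230 margin (10/230 and 27/230). Adjusting for the covariate in every sample removes it.

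**Step 7: error rate at the margin.** With the true difference at −230, non-inferiority should be declared 5% of the time. With confounders of d=0.4, r=0.25 all favouring non-inferiority, the screened analysis declares it about 7–8% of the time with one confounder, 10–11% with two and 12–15% with three. Fixed adjustment stays at 5–6%.

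**The case against.** The strongest reply is that the rule governs only a secondary/sensitivity model. It cannot change the primary t-test, and if confounding is the worry, the unadjusted primary test is the more exposed analysis. That is correct, and it limits the point to the quality of the check. It does not remove the point, because no other analysis in the plan addresses confounding in this comparison.

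The sentence before the rule may also intend a fixed adjustment, with screened variables added to it. The text permits that reading but does not settle it, so the plan needs clarifying either way.

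Three stronger readings are tempting, and the documents do not support them:
- A reader might infer that most moderate confounders are missed. That depends on values the plan does not give. At d=0.5, r=0.3 about two thirds are kept; the majority is lost only for weaker ones.
- A reader might take 35–69 fmol/punch as the bias the screen leaves. That is the bias with no adjustment at all; the screened figure is roughly 10–27.
- A reader might infer that the intervals are too narrow. For one confounder at d=0.4, r=0.25, coverage of the 90% interval after screening was 89.4–90.2%, against 89.6–90.5% with constant adjustment. The worst single-confounder case tried gave 88.1%.

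Finally, Section 9 describes itself as brief and defers to a fuller SAP due before database lock. That makes the change easy, but the screen is a stated rule and would carry forward unless replaced.

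**Conclusion.** The point holds as a cheap and worthwhile improvement to a secondary analysis. At about 49 versus 37 people the double screen drops roughly a third of confounders at d=0.5, r=0.3 and two thirds to three quarters at d=0.3, r=0.2–0.3, with higher losses when TFV-DP is truly lower. The bias left by one confounder is modest against the margin. It matters more when several act in the same direction, where false non-inferiority in the adjusted analysis reaches about 12–15% with three.

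These sizes rest on assumed d and r, normal covariates, the planned group sizes, and (for the error rates) confounders that all favour non-inferiority. The documents neither confirm nor exclude such confounders. Nothing here shows that the primary result is altered by the screen.

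**What to change.** In the SAP, delete the p<0.10 rule. Before the trial's TFV-DP results are examined, confirm which variables the MSM dataset holds and fix a short covariate set recorded in both cohorts. Age and race/ethnicity, from the plan's own list, are natural members; weight or creatinine clearance could be added if the MSM dataset has them. Adjust for the whole set regardless of p-value, and report the adjusted difference and its confidence interval against the 230 margin beside the unadjusted primary result. Use the same sentence to replace the general adjustment clause, so that only one model can be fitted.

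The cost is SAP wording and a few degrees of freedom: five single-term covariates reduce the residual degrees of freedom from 84 (86 − 2) to 79 (86 − 7). The real limit is the MSM dataset, which the documents do not describe. A confounder not recorded there stays unadjusted under any rule, and the report should say so.

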Hypothesis: Among transgender MAAB persons on csHT who report perfect adherence by iTAB in the past 34 days (ie, two intracellular half-lives) the mean intracellular tenofovir-diphosphate (TFV-DP) concentrations, as measured in DBS, will be equivalent to the levels of perfect adherence previously defined in MSM.

Sub-study I Secondary Objectives

- 1. To determine whether csHT interacts with PrEP in MAAB persons that would affect hormone effectiveness, measured by estrogen concentrations assessed at Weeks 0 and 12 of study follow-up.
 - **Hypothesis**: Among transgender MAAB persons on csHT, estrogen concentrations will not change significantly between baseline (Week 0) and Week 12 in individuals taking PrEP and receiving stable estrogen therapy (controlling for route and formulation).
- 2. To determine TFV-DP in MAAB of all adherence levels compared to not taking csHT, adjusting for confounding factors.
- 3. To determine TFV-DP in MAAB taking versus not taking antiandrogen medications (i.e., spironolactone, finasteride)
- 4. To measure the change in testosterone concentrations between baseline and Week 12 in female-assigned at birth (FAAB) taking PrEP and receiving stable testosterone therapy.
- 5. To determine emtricitabine-triphosphate (FTC-TP) concentrations (a measure of recent adherence) in TG / GNC persons of all adherence levels taking versus not taking hormones.
- 6. To determine changes in desired effects of csHT in TG / GNC persons taking PrEP as measured by the Body Image Scale (BIS).

Sub-study IV Objectives:

- 1. To determine the impact of genital STIs on CVF TFV levels.
- 2. To determine the impact of cytokine mediators of CV inflammation on CVF TFV levels.
- 3. To determine the impact of CV microbiome on CVF TFV levels.

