¹ Only for participants curre	ently taking	n PrFP Pai	rticinants red	uirina PrFI	P dispensation dur	ing an Interi	m visit v	vill rece	ive enou	ah PrFP

Only for participants currently taking PrEP. Participants requiring PrEP dispensation during an Interim visit will receive enough PrEP to last until the next regular study visit.

Adherence and Behavioral Assessments

We will measure adherence using the self-report daily text messages. These texts will include a personalized lead-in reminder message (e.g., "Those who are closest to you care about your health") and participants will be asked "Did you take your dose today? Reply: Y) Yes N) No P) Postpone". If 'Postpone' is selected, participants will receive a follow-up message 1 hour later asking them if they took their medication (Yes or No). Participants will also have the option of determining the word used to describe the study drug (e.g., 'med', 'dose', or other personal choice). Nonresponse or a 'No' response will be counted as not taking their dose. At each follow-up

² Participants with medication interruption greater than 14 days will require confirmation of HIV seronegative status prior to re-initiation of PrEP. Re-initiation must be achieved prior to the end of the week 36 visit.

³ Only for participants capable of becoming pregnant

⁴ Only for participants currently taking csHT. Baseline and Week 12 only.

⁵ STI screen only at week 24

⁶ Week 0 DBS collected only if participant is already taking PrEP at Baseline

⁷ Interim visit for: HIV testing if off PrEP for over 1 week and had high risk event, consider NAT or Ab/Ag; STI testing only if has symptoms (urethral discharge, genital sore); if seroconverted outside study; adverse event assessment

[†] UCSD-only sub-study evaluation. Additional specimens will be collected from anatomic site of positive GC at time of treatment. ♦ UCSD-only study extension

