The primary endpoint will be a composite adherence outcome determined by dried blood spot intracellular tenofovir diphosphate (TFV-DP) levels. A subject will be considered adherent if the TFV-DP levels are above 1246 fmol/punch (consistent with 7 doses in past week) at both week 12 and the last study visit over the 48 weeks. All randomized subjects that were dispensed PrEP at baseline will be included in the modified intent-to-treat analysis. Participants not achieving week 12 will be considered non-adherent.

Secondary Adherence Endpoints

A key secondary endpoint will be a composite outcome determined by TFV-DP levels at both week 12 and the last study visit associated with adequate adherence (>719 fmol/punch).

Self-reported adherence to PrEP through 48 weeks is defined as the proportion of text-reported doses over all possible doses in 48 weeks. Missing responses due to either missed text messages or early discontinuation of the study will be considered as no doses taken. Sensitivity analysis will also be done on the 'as-treated' population (i.e. treat missing as missing).

Additional self-reported adherence measure will be >90% adherence (i.e. on the ACTG 4-day recall at weeks 12, 24, 36, and 48); >90% dosing by VAS at each study visit.

- Poor adherence is defined as < 4 doses a week or discontinuation of study drugs. Subgroup analysis will explore the endpoint for discontinuation for reasons other than lack of risk or confirmed adverse event.
- Safety and tolerability outcomes are defined as incidence rates of: i) discontinuation of TDF/ FTC for any toxicity; ii) grade 2 or higher adverse event (symptoms or laboratory toxicity); iii) serious adverse events; iv) death

Randomization and Stratification

Subjects will be randomized (1:1) to one of two arms: the **iTAB** or the **iTAB+MI-B** enhanced adherence arm. Randomization will be stratified by clinic site, sex assigned at birth (male vs female), and prior history of PrEP use. Participants assigned "intersex" at birth will be included in the female group. A total of 300 subjects (150 per arm) will be randomized and followed in the study for 48 weeks after enrollment of the last subject.

Once eligibility and consent are confirmed, randomization will occur using the web-based CCTG data management system.

Study Power and Sample Size Justification

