Descriptive analysis will be performed for all the secondary outcomes. For comparisons between the two study arms, Fisher's exact test will be used for categorical outcomes; t-test or Wilcoxon rank sum test will be used for continuous outcomes. Multivariable logistic regression model will be used to study factors associated with poor adherence. Factors will include demographics, substance use, untreated mental illness, socieconomic status, low health/HIV and system literacy, fear of disclosure and non-English language. To evaluate changes in risk behavior after initiation of PrEP, descriptive summary will be provided for the number of HIV positive/unknown status partners and any unprotected anal intercourse with an HIV positive/unknown status partner by visit (at w12, 24, 36 and 48). Wilcoxon signed rank test will be used for comparison at each follow-up visit to the baseline visit. GEE model will be used to assess the change in risk behavior over time.

Safety analysis

Safety data will be reported for all the randomized subjects while they were taking or immediately (30 days) after taking study drug (as treated analysis). Tables will summarize the number of serious adverse events, adverse events (grade 2 or higher), PrEP discontinuation due to adverse events, by study arms and overall. Fisher's exact test will be used to compare the rates between the two groups. The time to TDF/FTC discontinuation due to adverse events will be compared between groups using the log-rank test and plotted using Kaplan-Meier curves.

SUB-STUDY I DESIGN

This pharmacologic sub-study will use the main study cohort to determine the interaction of cross-sex hormone therapy (csHT) on PrEP efficacy as measured by TFV-DP and FTC-TP DBS intracellular levels, and of PrEP on csHT effectiveness as measured by quantitative hormone levels in plasma.

SUB-STUDY I PROCEDURES

Subjects will be consented for participation in the sub-study at the main study's Screening Visit.

As part of the main study, plasma and DBS samples will be collected at Baseline and every 12 weeks. A Baseline DBS sample will be collected only if the subject is already on PrEP at the time of Baseline. Detailed concomitant hormone use, including route and frequency, will be collected at every clinic visit. Daily iTab responses will be used as a self-reported adherence measure.

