Other secondary analyses will explore further interactions between PrEP and csHT in MAAB we will perform analyses of the following potential interactions: a) TFV-DP in transgender persons (MAAB and FAAB) of all adherence levels compared to not taking csHT, b) TFV-DP in MAAB taking versus not taking antiandrogen medications (i.e. spironolactone and finasteride) and c) emtricitabine-triphosphate (FTC-TP) concentrations (recent adherence measure) in transgender persons of all adherence levels taking versus not taking hormones. These analyses will be analogous to the descriptive analyses in the primary outcomes. For FAAB transgender individuals, to determine the change between baseline and week 12 testosterone levels in individuals taking PrEP and receiving stable testosterone replacement (controlling for route, dose and formulation), we will use a paired test. For hormone therapy satisfaction, the main outcome of interest to these individuals is maintaining the physically desirable characteristics that the csHT provide. Thus, it is not the hormone levels that are as important

as the satisfaction with these traits. For the entire cohort of MAAB who are on stable csHT dosing (as defined as no change from baseline to week 12) from baseline to week 12 and from baseline to week 48 we will compare the hormone satisfaction with physical traits ranked for satisfaction using the BIS and summed for overall satisfaction score to compare between weeks 0, 12 and 48. Similarly, we will use the BIS for FAAB on stable csHT assessing physical traits compared at weeks 0, 12 and 48.

SUB-STUDY IV PROCEDURES

At Baseline, eligible participants will consent for additional sub-study sample collection on the main study informed consent form. Genital collection for *Neisseria gonorrhoeae* and *C. trachomatis* will be done at Baseline and Week 24 as part of the main study STI screening procedures.

For the sub-study, two genital swabs for microbiome and cytokine testing will be collected at Baseline and Week 24. Additional genital swabs for a vaginitis multiplex assay, herpesvirus and HPV testing as well as CVF collection via aspirator for TFV levels will be collected at Week 24.

Sub-study IV	Study Weeks of Follow-up					
Schedule of Evaluations	Screen	Wk 0	Wk 24			
Window	14 days	30 days	+/- 4 weeks			
Informed Consent	Х					
CV swab for cytokine testing		Х	Х			
CV Swab for microbiome		Х	X			
CVF collection for drug concentration TFV			X			

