integrase inhibitors, protease inhibitors or investigational antiretroviral agents) – if currently on TDF/FTC for PEP or PrEP they can switch to study provided drug but can not continue any other antiretroviral agent.

- Agents with known nephrotoxic potential:
 - aminoglycoside antibiotics (including gentamicin)
 - IV amphotericin B
 - cidofovir
 - o cisplatin
 - foscarnet
 - IV pentamidine
 - IV vancomycin
 - o oral or IV gancyclovir
 - other agents with significant nephrotoxic potential
- Drugs that slow renal excretion
 - Probenecid
- Immune system modulators
 - Systemic chemotherapeutic agents (i.e. cancer treatment medications)
 - Ongoing systemic corticosteroids (with the exception of short courses of tapering steroid doses for asthma or other self- limited condition).
 - Interleukin-2 (IL-2)
 - Interferon (alpha, beta, or gamma)
- Other agent known to have a significant interaction with TDF or FTC
- 6. Proteinuria 2+ or greater by urine dipstick
- 7. Pregnancy (if individual has a uterus)
- 8. Other condition that in the opinion of the investigator would put the participant at risk or interfere with participation, complicate interpretation of study outcome data, or otherwise interfere with achieving the study objectives.

Participation into Sub-study IV will be only be offered to a subset of 20 transgender men/gender non-conforming individuals with vaginas enrolled at the UCSD AVRC. Transgender women enrolled at the UCSD AVRC who have undergone gender reassignment surgery with neovaginas will also be offered participation, although we expect this number to be guite low.

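### The week 0 to week 12 hormone tests do not exclude or separate participants already on TDF/FTC at baseline, which pulls the mean change toward the hypothesised result of no change

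*Combined protocol and SAP*

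**What the plan says.** All references are to the combined protocol and SAP.

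- **Hypothesis** (section 6, Sub-study I Secondary Objectives, item 1): "estrogen concentrations will not change significantly between baseline (Week 0) and Week 12 in individuals taking PrEP and receiving stable estrogen therapy".
- **Estradiol test** (section 9, Sub-study Statistical Considerations, Analysis Plan): the aim is "to determine the change between baseline and week 12 estradiol levels in individuals taking PrEP and receiving stable estrogen replacement", and the method is given as "controlling for route, dose and formulation), we will use a paired t-test".
- **Testosterone test** (same plan, for participants assigned female at birth): the aim is "to determine the change between baseline and week 12 testosterone levels in individuals taking PrEP" on stable testosterone, again by a paired test.
- **Who is sampled** (section 9, schedule of evaluations, hormone footnote): "Only for participants currently taking csHT. Baseline and Week 12 only". The restriction is on hormone use, not on PrEP status.
- **Who may enrol** (section 10, Main Study Exclusion Criteria, item 5): "if currently on TDF/FTC for PEP or PrEP they can switch to study provided drug".
- **Baseline users are expected** (section 9, Sub-study I Procedures): "A Baseline DBS sample will be collected only if the subject is already on PrEP at the time of Baseline".
- **Randomization** (section 9): "Randomization will be stratified by clinic site, sex assigned at birth (male vs female), and prior history of PrEP use".

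The estradiol paragraph adds that levels will also be measured in people who choose not to start PrEP, and that regression models will be built if some factor calls for adjustment.

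**The concern.** The aim is to learn whether PrEP alters hormone levels. A within-person change from week 0 to week 12 answers that only if week 0 comes before PrEP. A participant who has taken TDF/FTC steadily for months has an on-drug value at both visits, so any lasting effect of the drug cancels. That participant still meets the analysis-set definition, which asks only for PrEP use and stable hormones.

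The direction of the bias matters more than usual here. The hypothesis is the absence of a change, the test is an ordinary paired test, and no equivalence margin is set. Dilution therefore makes the expected conclusion easier to reach. Section 9 calls the estradiol comparison the main secondary hypothesis of the sub-study, and section 7 describes worry about weakened hormone therapy as a possible major barrier to PrEP use. Falsely reassuring data would bear directly on that worry.

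**Working it through.** **Figure to reproduce.** There is none. The plan gives no sample size, effect size, SD or power for either hormone test. Its only Sub-study I sample size (45) belongs to the drug-level non-inferiority aim.

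**Inputs from the documents**
- Expected participants assigned male at birth on feminizing hormones: 70% of 280 = 196 (section 9, Sample Size and Power). This is an upper bound, before the stable-dose requirement, sub-study consent and attrition.
- Expected participants assigned female at birth: about 300 − 280 = 20.
- Significance level 0.05, unadjusted (section 9, Statistical Analysis Plan), taken as two-sided.

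**Inputs assumed**
- f, the share already on TDF/FTC at week 0 at stable exposure: 10% to 50%.
- True effect in new starters: a 20% fall, so δ = ln(0.8) = −0.223.
- SD of the log change: 0.8, so d = 0.223/0.8 = 0.279. The log scale is also an assumption; the plan does not name a scale.
- A smaller case of 100 pairs, to show sensitivity to n.

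**Step 1, size of the bias.** If baseline users have no PrEP-induced change, the pooled mean log change is (1−f)δ and the apparent fall is 1 − 0.8^(1−f). For f = 10%, 20%, 30%, 40%, 50%, a true 20% fall appears as 18.2%, 16.3%, 14.5%, 12.5%, 10.6%.

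**Step 2, power.** Paired t-test, noncentral t, with noncentrality
- pooled: (1−f) · d · √n
- restricted to new starters: d · √(n(1−f))

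Example, n = 100 and f = 30%: pooled 0.7 × 0.279 × 10 = 1.95; restricted 0.279 × √70 = 2.33.

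| f | 100 pairs: pooled | 100 pairs: restricted | 196 pairs: pooled | 196 pairs: restricted |
|---|---|---|---|---|
| 0 | 0.79 | 0.79 | 0.97 | 0.97 |
| 10% | 0.70 | 0.74 | 0.94 | 0.96 |
| 20% | 0.60 | 0.69 | 0.87 | 0.93 |
| 30% | 0.49 | 0.63 | 0.78 | 0.90 |
| 40% | 0.38 | 0.57 | 0.64 | 0.85 |
| 50% | 0.28 | 0.49 | 0.49 | 0.78 |

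The pooled columns keep the SD at 0.8. Allowing for the extra variance of a mixed group, SD = √(0.8² + f(1−f)δ²), lowers each by less than 0.01.

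**Step 3, does the ranking depend on the assumptions?** Pooling multiplies the noncentrality by (1−f); restricting multiplies it by √(1−f), which is larger for any f between 0 and 1. Apart from the small loss of degrees of freedom, restricting is better on power as well as bias, whatever the SD or n, as long as baseline users carry no change.

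**Step 4, testosterone.** With 20 pairs and the same assumptions, power is 0.22 undiluted. At f = 30% it is 0.13 pooled and 0.16 restricted (14 pairs).

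**The case against.** The case on the other side has five parts.

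1. *The documents never say that baseline users stay in.* True; it is an inference. The mention of people who choose not to start PrEP suggests that the intended contrast is initiation, and section 9 describes itself as a brief account to be followed by a fuller SAP. But eligibility, the sampling rule and the analysis-set wording all admit these participants, and nothing removes them. Applied as written, the plan pools them.

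2. *The plan has a route to adjustment.* The estradiol paragraph points back to an earlier analysis labelled 3A. If that means the preceding regression, it adjusts for stratification variables, and PrEP history is one. However, the clause is conditional, the label is undefined, past use is not current use, and the testosterone paragraph does not repeat it. Stratified randomization balances the arms; it does not repair a within-person change. The non-initiator series has no stated comparison and would not remove baseline users from the paired test.

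3. *A reader might infer that baseline users must show zero change whatever PrEP does.* The documents do not support that. People on TDF/FTC for PEP may have started recently, and daily text support could raise exposure by week 12. The factor (1−f) is the full-dilution case; the real bias may be smaller.

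4. *The loss may be modest.* This stands. At 196 pairs and f of 10% to 20%, restricting gains only 2 to 6 percentage points of power. The large losses need a high f or fewer pairs.

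5. *This is a secondary objective of a sub-study.* Also true. It does not touch the trial's primary endpoint or the sub-study's drug-level outcome.

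**Conclusion.** The point holds as a gap in the definition of the analysis set. Neither paired hormone test excludes or separates participants already on TDF/FTC at baseline, and including those at stable exposure biases the mean change toward zero, in the direction of the hypothesis. The bias is at most a factor (1−f). Its actual size cannot be fixed from the documents, because f, the effect and the SD are all unstated; the figures above are illustrations over a range.

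Two further readings are tempting and should be resisted. The estradiol power figures cannot be carried over to testosterone: with about 20 people expected, and only those on stable testosterone entering, that test has little power however the set is defined. Nor can the baseline dried blood spot confirm who is unexposed, because it is drawn only from people already known to be on PrEP.

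**What to change.** State in the SAP that both paired week 0 to week 12 hormone tests include only participants not taking TDF/FTC, for PrEP or PEP, at baseline according to the medication history already collected. Report baseline users separately as a stable-exposure group, using their baseline dried blood spot to confirm exposure. Give the number in each group, so that f becomes known.

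The cost is a change of wording and fewer pairs in each test; no new data are needed. Misclassification of undeclared users would remain, since no baseline drug level is planned for those who do not report PrEP use.
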